including seizure frequency, seizure type, seizure onset, medication history, family history of seizure, and also developmental stages, will be recorded from electronic medical record. Besides, the CT-scan or MRI are also collected from the same source. After that, their quality of life will be assessed by QOLCE-55 validated questionnaire through self-guided report. Furthermore, the laboratory investigation and EEG will be performed.

The next phase is intervention phase, started from initial step and ended by the maintenance of new combination therapy, which takes with overall 12 weeks. Initially, the substitution drugs with each initial dose are consumed. The drugs consist of valproic acid for the generalized and carbamazepine for focal epilepsies. On the other hand, the control group will take lamotrigine or clobazam for generalized and oxcarbazepine for focal ones. The phase continuous to titration dose, in which, the dose is raised gradually until it causes 50% of seizure reduction, and the next step is maintained the dose for about 2 weeks.

The following is tapering-off and after that stopping the substituted drug, levetiracetam or topiramate, which is determined by considering individual condition. Yet, if the seizures increase more than one and a half time of the previous frequency during the phases, the intervention will be ended immediately. On the contrary, if the condition is better, then the children go to the maintenance of new combination, that is the substitution drug and the old drugs in which the seizures do not go up or even better keep going down. The children who complete all of the phases are categorized as responder. In case if the intervention is ended, the subjects will be given the former combination therapy with adjusted doses in order to decrease the seizures until reaching the pre-intervention condition. The subjects are categorized as non-responder, and will be dropped-out. The other criteria of drop-out are resignation, non-compliance of study procedure, and death in term of other causal not related to the study. While in term of lost to follow-up, is intended for those who do not attend the study without any possible reasons.

[figure not shown]

Figure 2. flow-chart of the study

Maintenance the dose of the new combination therapy that consist of the new drug and

Maintenance

old drug after stopping the substituted drug

Inclusion criteria

- 1. Children age at 1 18 years old

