The test is performed in hospitals' laboratory where the study take place and is done twice, at the baseline and post intervention phase. The order of the blood test consists of complete blood test, liver function test including alanine and aspartate transaminase, kidney function test including urea and creatinine, and also blood electrolyte that consist of natrium, kalium and calcium. The laboratory professional takes the blood from vein of the arm. The subjects are seated or lying down, accompanied by the parents, while for the younger children, they seat on his/her parents' lap or position that make them feel comfortable. Older children may be asked to make a fist and then will be tied by a rubber band around his/her arms. After that, the needle is inserted the needle until the blood is drawn. The laboratory worker will take the needle since the amount of blood is enough and puts an adhesive bandage over the site. The next step is analyzes of the sample and the result will be issued for about 1-2 days both printed or provided on the electronic medical record.

Electroencephalography Examination

The EEG examination is operated two times, at the baseline and post intervention phase, with high density machine (Caldwell Easy III) is done twice, pre- and post-intervention. The machine will operate for about 45 minutes including 5 minutes each for eye-open and eye-close in every subjects. Beginning with acquisition, EEG recordings use standard parameter to analyze brain activity at various frequencies to gain good quality and artefact-free result. The printed results of the EEG is available for about 4-7 days after the examination.

Data collection

All relevant data will be recorded, by nominated member(s) of the research team, on a case report form (CRF). Each participant will have a CRF and be assigned a unique identification number.

Baseline data

At entry into the study, the following baseline information will be recorded in the CRF:

- unique patient identification number contact telephone number and/or email address
- date of entry into the study
- eligibility for study entry based on inclusion/exclusion criteria
- age at study entry, in years and months
- gender
- weight and height
- seizure type (eg, generalized tonic clonic, absence, myoclonic and partial)
- the age at diagnosis and duration of epilepsy
- seizure frequency or average number of seizures per month

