- current anticonvulsant(s) with doses and formulation and its side effect (if presents)
- other medications and its side effect (if presents)

- first recognized seizure date
- prior EEG and laboratory which has been performed at the baseline phase
- physical examination

Follow-up data

Follow-up data will be collected during regularly scheduled clinic visits (per 2 weeks). This information will be obtained from the participants' diary card. Important information to be collected at follow-up will include:

- physical examination
- adverse drug reaction of the substitution therapy that happen
- seizure's frequency
- type of seizure
- complaint

Outcome evaluation

- a. The difference in responders was the difference in the percentage of responders in the group that used first line OAE again as substitution therapy and those that used standard therapy. Responders are subjects who experience a decrease frequency of seizure more than or equal to 50% of the initial seizure. Frequency of seizure is the number of seizures that occur within 1 month. In previous studies, it was said that the frequency of seizures was said to have decreased significantly or was said to respond if the seizures were reduced by 50% or more from the initial seizure. ^{19, 29} Based on this, researchers will categorize the frequency of seizures into:
 - Responder: there is a decrease in the frequency of seizures by 50% or more than before
 - Non-responder: namely the frequency of seizures remains or decreases but not up to 50% of the initial seizure frequency or the frequency is more than before

Furthermore, the proportion in the form of the percentage of respondents in the two groups is calculated and differentiated, therefore it is classified into two groups:

- Different : when a significant difference is shown in difference of proportion test of the 2 unpaired groups.
- Not different: when there is no significant difference is shown in difference of proportion test of the 2 unpaired groups.

- b. Differences in quality of life: quality of life assessment using QOLCE-55 instrument. The average of each function (cognitive, emotional, social and physical functions) and the average of the total functions are assessed. This variable is categorized into:
 - Different, if there is a difference in the average quality of life
 - Not different, if there is no difference in the average quality of life
- c. Differences in electroencephalography appearance

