EEG recording results are categorized into:

- Normal: does not show of hypofunction/asymmetry/epileptiform waves
- Abnormal: shows a picture of hypofunction/asymmetry/epileptiform waves or a combination of 1 or more of these features

The subjects who show changes in their EEG are later grouped into groups of abnormal to normal or abnormalities that showed improvement. Abnormalities that show improvement, for example are hypofunction (slowing down) waves experience improvement or decreasing number of epileptiform waves.

Next, a proportion calculation is carried out in the form of the percentage to subjects who experience a change in the EEG and will be categorized into:

- Different : when a significant difference is shown in difference of proportion test of the group that reuses first line OAE line as substitution therapy and those that use standard therapy/
- Not different: when there is no significant difference is shown in difference of proportion test of the 2 groups.
- d. Difference in actual failure between the groups reusing first line OAE as substitution therapy and those taking standard therapy. Description of drug side effects in the form of frequency distribution and percentage of side effects in each group. Description of laboratory results in the form of frequency distribution and percentage of side effects in each group
- e. Factors contributing to decrease in seizure frequency (age, seizure onset, seizure type, family history of seizures, developmental delay, history of OAE, initial seizure frequency, initial EEG, structural brain abnormalities)

Sample size

The estimated sample size in this study was calculated using the different proportion formula for the 2 unpaired groups as follows ²⁹:

$$n1 = n2 = (\frac{Z_{\alpha}\sqrt{2PQ} + Z_{\beta}\sqrt{P1Q1 + P2Q2}}{P1 - P2})^{2}$$

Description:

n1 number of subjects who received the new drug (First Line OAE)

n2 number of subjects receiving standard drug (Second line OAE)

Alpha type one error (5%)

Zα alpha standard value 5% one-way hypothesis (1,96)

Beta type two error (20%)

Zβ beta default value 20% (0,84)

P2 proportion of decreased seizures on standard drugs (reference) for example 0.7

Q2
$$1-P2 = 1-0.7 = 0.3$$

P1-P2 difference in the proportion of reduced seizure that is considered significant between the new drug and the standard (defined by the researcher) for example 25% (0.25)

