This test will use 2 analyses known as intention to treat analysis and per-protocol analysis. Intention to treat analysis means that all research subjects who have been randomized are included in the analysis according to their initial allocation regardless of whether or not the subject is taking the drug/therapy being tested or a placebo, or whether these subjects died before taking the drug being tested. Subjects who did not

failure.

take medication, lost to follow-up, and who moved to another group, are considered failures of their original group.

Whereas per protocol analysis only includes subjects who complete the research to the end.

- 4. Analysis of the difference in time to achieve a decrease in seizure frequency with the chisquare test or if it does not meet the requirements, an alternative test is performed, namely the Mann-Whitney test
- 5. Analysis of clinical characteristics, side effects of OAE, and laboratory findings of complete blood count (hemoglobin, hematocrit, leukocytes, platelets, and type count), liver function (SGOT and SGPT), kidney function (urea and creatinine), and blood electrolytes (sodium, potassium, calcium, chloride) in pediatric epilepsy patients who are resistant to combination second OAE who re-use first line OAE as substitution therapy and who use standard therapy (secondary outcome). All existing data is processed and presented in a table consisting of mean and standard deviation or median and inter-quartile range, as well as frequency distribution.
- 6. Analyzing factors that affect the decrease in the frequency of late seizures (age, seizure onset, seizure type, family history of seizures, developmental delays, history of OAE, initial seizure frequency, initial EEG, brain structural abnormalities) in pediatric patients with resistant epilepsy combination of second line OAE who re-use first line OAE as substitution therapy (secondary outcome).

Data is categorical. Data is analyzed using Chi-square statistical test, if results do not meet the requirements then an alternative test will be performed, known as Fisher's multivariate test and further analyzed with multivariate test and logistic regression analysis. The significance level (α) is 5% and the research confidence level is 80%. Results will show statistically related if value of $p \le \alpha$ is obtained.

Ethics and dissemination

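### The factor analysis treats age, seizure onset and initial seizure frequency as categories although they are collected as numbers, and it fixes no cut points

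*Combined protocol and SAP*

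**What the plan says.** Statistical Analysis, item 6, sets out the factor analysis: "Analyzing factors that affect the decrease in the frequency of late seizures (age, seizure onset, seizure type, family history of seizures, developmental delays" and so on, nine factors in all. The list includes age, seizure onset and initial seizure frequency. Item 6 applies to the children who receive a first-line drug again, planned at 50.

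The method follows in one paragraph: "Data is categorical. Data is analyzed using Chi-square statistical test", then a Fisher test if the chi-square conditions fail, and then the factors are "further analyzed with multivariate test and logistic regression analysis". The significance level is 5%. Outcome evaluation, e, repeats the list ("Factors contributing to decrease in seizure frequency (age, seizure onset, seizure type" and the rest) and adds nothing on coding.

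The Baseline data list shows how the three variables are recorded:
- age: "age at study entry, in years and months", with eligibility spanning 1 to 18 years under Inclusion criteria;
- onset: "first recognized seizure date", from which age at onset can be derived;
- initial frequency: "seizure frequency or average number of seizures per month".

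No cut point, number of groups or reason for grouping is given for any of the three.

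**The concern.** Chi-square and Fisher tests need grouped factors, so item 6 cannot be run on age, onset or initial frequency until someone chooses the groups. That has two costs. Grouping discards information, which lowers the chance of finding a factor that really matters. An open choice of cut point, if made after the data are seen, raises the chance of declaring a factor that does not matter.

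Explaining which factors influence seizure reduction is one of the Secondary Objectives. The logistic regression already in the plan accepts all three variables uncut. Elsewhere the plan does keep numbers as numbers: item 2 uses a t test or Mann-Whitney test for quality of life.

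**Working it through.** **Plan's own figure.** None exists to reproduce. The plan gives no effect size or power for item 6.

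**Inputs from the documents.** First-line arm n = 50; alpha 5%. Response rates from Sample size: 0.70 (standard drug), 0.95 (new drug), average (0.95 + 0.70)/2 = 0.825.

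**Assumptions, not in the documents.** Two-sided test; one factor at a time; uniform factor unless stated; effect linear in the log-odds; split at the median; Fisher used when an expected count is below 5; seizure onset read as age at onset.

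**Step 1: approximate loss.** A median split keeps a fraction E of the information: 0.75 for a uniform factor, 2/π = 0.637 for a normal one. If the uncut test has power 80%, then

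power after split = Φ[(1.96 + 0.84)·√E − 1.96]

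- uniform: 2.80 × 0.866 − 1.96 = 0.47, power 68%, loss 12 points;
- normal: 2.80 × 0.798 − 1.96 = 0.28, power 61%, loss 19 points.

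For a uniform factor the same formula gives a loss of 4 points when uncut power is 20%, and 7 points when it is 95%. The loss is largest in the middle range.

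**Step 2: simulation at n = 50.** Likelihood-ratio logistic test on the uncut factor against a median split with chi-square or Fisher; 2,500 runs per cell, error about 1 point, except the row marked *, which used 1,500 runs.

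| Response | Odds ratio per SD | Uncut | Median split | Loss (points) |
|---|---|---|---|---|
| 70% | 1.5 | 28% | 22% | 6 |
| 70% | 2.0 | 58% | 43% | 15 |
| 70% | 2.5 | 78% | 66% | 12 |
| 82.5% | 1.5* | 20% | 13% | 7 |
| 82.5% | 2.0 | 44% | 26% | 18 |
| 82.5% | 2.5 | 61% | 39% | 22 |
| 95% | 2.0 | 19% | under 1% | about 18 |
| 95% | 2.5 | 27% | 1% | 26 |

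A repeat at 82.5% with 1,500 runs gave losses of 14 and 22 points at odds ratios 2.0 and 2.5, so each loss is good to a few points. About 12 to 20 is a fair summary for moderate effects at 70% to 82.5%.

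If both arms were pooled (n = 100, response 82.5%), odds ratios 1.5, 2.0 and 2.5 give 33%, 70% and 88% uncut against 25%, 56% and 77% split: losses of about 8, 13 and 12 points.

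**Step 3: free cut points.** With no true effect and n = 50 at 70% to 82.5% response, taking the best of three quartile cuts gives about 10% false positives. Taking the best of seven cuts between the 20th and 80th percentiles gives 12% to 20% at response rates of 50% to 82.5%.

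**Step 4: the planned 95% response.** Expected non-responders: 50 × 0.05 = 2.5. For a 25/25 split with all k non-responders on one side, the smallest two-sided Fisher p is 2·C(25,k)/C(50,k):
- k = 2: 2 × 300/1,225 = 0.490
- k = 3: 2 × 2,300/19,600 = 0.235
- k = 4: 2 × 12,650/230,300 = 0.110
- k = 5: 2 × 53,130/2,118,760 = 0.0502

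With five or fewer non-responders an even split therefore cannot reach p ≤ 0.05. An uneven split can: for 10/40 with all 3 non-responders in the smaller group, p = C(10,3)/C(50,3) = 120/19,600 = 0.006.

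The uncut likelihood-ratio test also struggles here. Its power is 19% to 27% in the table, and its false-positive rate is about 7.6% against a nominal 5%.

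**The case against.** The strongest reply is that item 6 ends in logistic regression, gives no covariate coding and does not forbid continuous terms. The statement that data are categorical may also refer to the outcome, as the similar statement in item 1 does. This stands in part: a reader might infer that the plan rules out continuous terms in the model, and the text does not say so. But the chi-square or Fisher step cannot be run on an ungrouped factor, and its p values are to be read against 5%.

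The power loss is also conditional. A reader might infer that grouping always costs 10 points or more. It does not: weak effects, or power near its ceiling, lose about 4 to 9 points. If the true effect is a step at the median, grouping does slightly better. At n = 100, response 82.5% and odds ratios of 3 and 4 across the step, the split has 44% and 64% power against 41% and 59% uncut.

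Two further inferences go too far. Silence on cut points is no evidence that they will be picked to suit the data, so the 10% describes what the wording allows. Nor can it be said that Fisher's test can never detect an age effect at 95% response. That holds for an even split, which the plan does not specify, and the root cause there is the small number of non-responders, which affects any balanced binary factor too.

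Finally, reading seizure onset as age at onset is an inference. It is reasonable because seizure type is listed separately and a first seizure date is collected.

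**Conclusion.** The point holds as a low-cost improvement to a secondary analysis. Item 6 pushes three numeric factors through tests for categories without saying how they are to be grouped.

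The 12 to 20 points rest on the median split and the linear effect assumed above, and on a first-line response of 70% to 82.5%, below the 95% the plan hopes for. At 95% the split has almost no power, but keeping the variables continuous rescues little, so results there should be labelled exploratory whichever coding is used.

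A reader might infer that the trial's main conclusion is at risk. The documents do not support that: the responder comparison and the sample size do not depend on item 6.

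**What to change.** In item 6, replace the statement that the data are categorical with:

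> Age, age at seizure onset and initial seizure frequency (log-transformed if skewed) are analysed as continuous variables in the logistic regression, with odds ratios and 95% confidence intervals. Chi-square or Fisher tests are used only for factors that are categories by nature: seizure type, family history, developmental delay, history of OAE, initial EEG and structural brain abnormality. Any grouped table of the numeric factors is descriptive only.

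This places all nine factors: three numeric and six categorical. Add that the results are exploratory if non-responders are very few.

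The cost is a few sentences, with no new data and no new type of model. There are two downsides. Linearity in the log-odds is assumed, and this can be checked. Likelihood-ratio p values are unreliable with only a handful of non-responders, where a penalised or exact logistic fit can be used instead.

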STUDY PROTOCOL

THE EFFICACY AND SAFETY OF FIRST LINE ANTI-EPILEPTIC DRUGS (AEDs) AS SUBSTITUTION THERAPY FOR CHILDREN WITH DRUG RESISTANT EPILEPSY

Protocol Number 22-09-1097

ABSTRACT

Background: Drug resistant epilepsy occurs around 30% of children with epilepsy. It is the failure to get seizure-free after combining two or more anti-epileptic drugs whether first- or second-line ones. Previous studies focus on the efficacy and safety between the two groups whether as add-on or substitution therapy mostly in newly diagnosed epilepsy children. However, the study that investigate first line Anti-epileptic Drugs (AEDs) as substitution therapy compared to second-line ones particularly among drug resistant epilepsy children is still lack. **Design**: It is an open-label, randomized controlled trial, which will be conducted in three referral hospitals in Jakarta, Cipto Mangunkusumo, Harapan Kita, and Fatmawati Hospital, from November 2022 until April 2023. The data will be collected from electronic medical record consisting of demographic, clinical characteristics, and brain CT scan or brain MRI, and diary cards that record daily drug consumption and adverse drug reaction. Self-administered QOLCE-55 questionnaire is used to assess the quality of life of the children. Furthermore, there will be EEG and laboratory examination prior and after intervention. The data will be recorded on Case Report Form that is filled by the researcher. Ethics committee approval is obtained from The Ethics Committee of The Faculty of Medicine, University of Indonesia-Cipto Mangunkusumo Hospital. Research permits would be issued by each institution where the study will take place.

Sample: There will be 100 participants, divided into 2 groups, the intervention and control. Fifty children in the intervention group will be treated with first line AEDs as the substitution therapy, while the other 50 participants in the control group will get second-line AEDs. The sample size is calculated based on the difference proportion of two independent groups.

Duration of the study: The study will take 14 weeks as a whole that consists of 6 phases including baseline, initial, titration, maintenance, tapering-of, stopping and another maintenance phase.

Introduction

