Randomized studies in drug-resistant epilepsy typically involve addition of new anti-epileptic drugs. However, in clinical practice, if the patient is already taking multiple drugs, then substitution of one of the current medications commonly occurs, despite little evidence supporting this approach.²² The choice of the substitution drug depends on the mechanism of action, the pharmacokinetic profile, drug-drug interaction, and the risk of seizure exacerbation as well as patients-related factors. The new combination is intended to maximize efficacy and minimize toxicity. However, the availability and cost-effectiveness should also be

taken into consideration since the patient would not reach the goal of ideal combination of drugs if they could not afford it nor even get the medication. ²³⁻²⁶ Another considerable case is one of drug resistance patterns in which at the first-time patients may not responsive to treatment yet they change into a state that is responsive to the medication. ²⁷ The choice of substitution therapy may originate from firs-line AEDs since evidences have shown they have equal efficacy to those of second-line ones. However, there is still lack of evidence whether the drug resistance pattern occur if the substitution drug is originated from first-line AED even more if it has ever been given prior to the current drug combination. ²⁷ The study aims to analyzed the efficacy and safety of first-line AEDs as substitution therapy in drug-resistant epilepsy children.

Primary Objective

The primary outcome of the research is to analyze the proportion of responders, who are defined as subjects who get 50% of seizure reduction.

Secondary Objectives

There are some secondary objectives of the study. The first one is to analyze the differences of improvement of quality of life, EEG feature and time to achieve seizure reduction, between the intervention and the control group. Besides, the research will describe the clinical characteristics, adverse effects of the drugs and laboratory features related to the adverse effects, among children with drug-resistant epilepsy. Furthermore, it will explain factors influencing the reduction of seizure frequency

Study Design

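### The nine-factor logistic analysis is confined to the first-line arm, where the rate used to size the trial leaves about 2.5 non-responders, too few to estimate or detect any factor

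*Combined protocol and SAP*

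**What the plan says.** Under Secondary Objectives, the protocol says "it will explain factors influencing the reduction of seizure frequency". Outcome evaluation, e, lists "Factors contributing to decrease in seizure frequency". Neither limits the question to one arm.

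Statistical Analysis, item 6, names nine factors: "age, seizure onset, seizure type, family history of seizures, developmental delays, history of OAE, initial seizure frequency, initial EEG, brain structural abnormalities". Its population is children "who re-use first line OAE as substitution therapy (secondary outcome"). Item 5, directly above, covers children "who re-use first line OAE as substitution therapy and who use standard therapy (secondary outcome"), and items 1 and 3 also name both groups. Item 6 is therefore narrower than the objective it serves, and no reason is given.

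Item 6 declares the data categorical. It prescribes chi-square, or Fisher where chi-square is unsuitable, after which the factors are "further analyzed with multivariate test and logistic regression analysis" at a 5% level. It gives no rule for which factors enter the model, no analysis set, no cut-points and no method for sparse outcomes.

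**The concern.** A logistic model is limited by the rarer outcome, here non-response. The one-arm restriction confines the analysis to the arm in which the design assumes non-response is rarest. With so few non-responders, some combination of factors will often separate responders from non-responders perfectly. Maximum likelihood then has no finite solution, yet standard software may still print extreme odds ratios that could be published as predictors. The univariate tests fare no better, because with a handful of non-responders they may be unable to reach significance whatever the data show. A stated secondary objective would then go unanswered.

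Treating everything as categorical discards further information. The Baseline data list records age in years and months, the date of the first recognised seizure, and seizures per month.

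**Working it through.** **Inputs.** Abstract: "Fifty children in the intervention group will be treated with first line AEDs as the substitution therapy", with 50 more in the control group. Sample size section: response P1 = 0.95 on first-line drugs and P2 = 0.70 on standard drugs, z-values 1.96 and 0.84, and a 10% dropout allowance giving 110 in total (55 per arm).

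**The plan's own figure.** With Q1 as printed (0.5):

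- 1.96 × √(2 × 0.825 × 0.175) = 1.053
- 0.84 × √(0.95 × 0.5 + 0.7 × 0.3) = 0.695
- ((1.053 + 0.695) / 0.25)² ≈ 48.9, against the stated 49.56, rounded to 50.

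The figure is reproduced to within two patients. The printed Q1 is a slip, since 1 − 0.95 = 0.05; with 0.05 the formula gives 35.0, so 36 per arm. That is a separate matter, and it does not imply 50% non-response in the first-line arm.

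**Expected non-responders**

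- First-line arm: 50 × 0.05 = 2.5; per factor 2.5 / 9 = 0.28.
- Both arms: 50 × 0.05 + 50 × 0.30 = 17.5; over nine factors plus an arm term, 17.5 / 10 = 1.75.
- The restriction leaves out 15 of these 17.5 (86%).

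**Binomial probabilities, n = 50, non-response 0.05.** None: 0.95^50 = 7.7%. Three or fewer: 76%. Five or fewer: 96%.

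**Can the univariate test detect anything?** Take a factor splitting the arm 25/25, with all k non-responders on one side. The smallest attainable two-sided Fisher p is 2 × C(25,k) / C(50,k):

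| k | smallest p |
|---|---|
| 2 | 0.49 |
| 3 | 0.23 |
| 4 | 0.11 |
| 5 | 0.0502 |

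Such a factor cannot reach p ≤ 0.05 with five or fewer non-responders, which is 96% of trials, even under a perfect association.

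**Can the model be fitted?** Separation was checked by linear programming in simulated trials. Assumptions not in the documents: independent binary factors with no true effect, each with prevalence between 0.5 and 0.2. The ranges below span those prevalences.

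| Setting | Expected non-responders | Per factor or term | No finite estimate |
|---|---|---|---|
| First-line arm, 95% response, nine factors | 2.5 of 50 | 0.28 | about 90–99% |
| Same, three factors | 2.5 of 50 | 0.83 | about 66–92% |
| First-line arm, 70% response, nine factors | 15 of 50 | 1.7 | about 0–30% |
| First-line arm, 10% dropouts counted as failures, nine factors | 55 × (0.10 + 0.90 × 0.05) ≈ 8 of 55 | 0.9 | about 15–80% |
| Both arms, nine factors plus arm | 17.5 of 100 | 1.75 | about 7–26% |

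The pooled model still fails sometimes, in part because in 7.7% of trials the first-line arm has no non-responder and the arm coefficient itself is then infinite.

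**The case against.** **The 95% is not a forecast.** This stands. It is the reference rate plus the smallest difference of interest, and both inputs are given as examples. A reader might infer that the plan predicts two or three non-responders; the documents support only that this follows at the rate used for sizing. At 70% response the model can usually be fitted, but on 1.7 events per factor.

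**Dropouts may count as failures.** Item 3 counts untreated, lost and crossed-over subjects as failures of their original group. Item 6 names no analysis set, so it is open whether the rule applies. If it does, failure of the fit depends heavily on factor prevalence, and the model would partly predict dropout. At the other extreme, the Study procedure section classes those who complete all phases as responders, so a completers-only set under that wording would contain no non-responders.

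**Not all nine factors need enter.** This also stands. A reader might infer a 5% screen for model entry, but item 6 states neither a screen nor a full model. Entering fewer factors does not rescue the fit at 95% response, as the three-factor row shows.

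**Multiplicity.** A reader might compute 1 − 0.95⁹ = 37% as the chance of a false factor. That needs nine independent tests each reaching a full 5%, which so few non-responders do not allow. In simulation at 95% response the chance is about 5–12%, depending on factor prevalence and on when Fisher replaces chi-square.

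**The investigators may want predictors of response to first-line re-use specifically.** That is a legitimate question, but neither the objective nor outcome e poses it, and the planned arm is too small to answer it at the sizing rate.

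**Conclusion.** The concern holds in a conditional form. At the response rate that sizes the trial, with all nine factors entered and dropouts not counted as failures, the item 6 model would have no finite maximum-likelihood solution in about 90–99% of trials, and an evenly split factor would be undetectable by Fisher's test in 96%. Under more favourable assumptions the model can be fitted more often, but it still rests on fewer than two events per factor. The simulated ranges depend on the assumed independent binary factors.

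A reader might infer that half the trial's data are thrown away. They are left out of this secondary analysis only, and the primary comparison is unaffected. The harm is inability to estimate or detect factors rather than a flood of false positives. The mismatch between item 6 and the unrestricted objective and outcome e is there whatever the response rate.

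**What to change.** Rewrite item 6 as follows:

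- Fit one logistic model on all randomised children, with treatment arm as a term, using Firth (penalised) estimation.
- Enter age, seizure onset and initial seizure frequency as continuous variables.
- Do not select factors by univariate p-value.
- Say how dropouts are coded in this analysis.
- Report odds ratios with 95% confidence intervals, labelled exploratory.

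Penalisation and the exploratory label are essential, because pooling alone leaves about 1.75 events per term. A shorter prespecified list of factors would help further.

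The cost is SAP wording, since the factors and the outcome are already collected in both arms. The downside is real: the model estimates factor effects shared across the two treatments, not effects specific to first-line re-use, and the estimates will remain imprecise.
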